8. DATA ANALYSIS/STATISTICAL METHODS

Detailed methodology for summary and statistical analyses of the data collected in this study will be documented in a Statistical Analysis Plan (SAP) and will be maintained by the sponsor.

The number and proportion of subjects with *S. pneumoniae* isolates detected will be summarized for both cohorts: the 13vPnC cohort and unvaccinated cohort. Additionally, the number and proportion of each serotype, serotype included in 13vPnC (VT), and serotypes not included in 13vPnC (non-VT) will be summarized for both cohorts.

For each cohort, children will be assigned to 2 groups: Participant in whom a 13vPnC vaccine type (VT) strain has been isolated from the respiratory tract, and participant from whom a 13vPnC VT strain has not been isolated from the respiratory tract (VT carrier versus without VT carrier). Therefore, a total of 4 subgroups are available: 13vPnC cohort with VT carrier; 13vPnC cohort without VT carrier; unvaccinated cohort with VT carrier; unvaccinated cohort without VT carrier.

For each of the 13 serotypes contained in 13vPnC, the IgG concentration and MOPA titers will be transformed in logarithm scale. Crude geometric mean concentrations (GMCs) and geometric mean titers (GMTs) and 95% confidence interval (CI) will be calculated for the 4 cohort/carriage subgroups.

A multiple regression model will be used with the log concentration or log titers as a dependent variable. Independent variables will include cohort (13vPnC or unvaccinated), 13vPnC VT carriage status, and the interaction of the cohort and carriage status, as well as the confounding variables (age at enrollment, residence location, season of enrollment). Adjusted GMCs (or GMTs) and adjusted geometric mean ratios (GMRs) along with 95% CI will be estimated based on this model. The (GMRs) will compare antibody levels between any 2 of the 4 subgroups, as well as between the 2 cohorts, and between the carriage status.

Additionally, serotype-specific GMC/GMT (or adjusted GMC/GMT) and 95% CI may be provided for each 13vPnC serotype carriage status (Yes/No), for both 13vPnC cohort and unvaccinated cohort. Similar to any 13vPnC VT carriage status, the descriptive comparisons will be presented as GMR (or adjusted GMR) and 95% CI.

All of the analyses are considered as descriptive and no multiplicity adjustment will be made.

8.1. Analysis Timing

As this is a descriptive study, data may be summarized on an ongoing basis.

9. QUALITY CONTROL AND QUALITY ASSURANCE

Pfizer or its agent will conduct periodic monitoring visits during study conduct for studies conducted at non-Pfizer investigator sites, to ensure that the protocol and Good Clinical Practices (GCPs) are being followed. The monitors may review source documents to confirm that the data recorded on CRFs are accurate. The investigator and institution will allow Pfizer monitors/auditors or its agents and appropriate regulatory authorities direct access to source documents to perform this verification. This verification may also occur after study completion.

During study conduct and/or after study completion, the investigator site may be subject to review by the Institutional Review Board (IRB)/ethics committee (EC), and/or to quality assurance audits performed by Pfizer, or companies working with or on behalf of Pfizer, and/or to inspection by appropriate regulatory authorities.

The investigator(s) will notify Pfizer or its agents immediately of any regulatory inspection notification in relation to the study. Furthermore, the investigator will cooperate with Pfizer or its agents to prepare the investigator site for the inspection and will allow Pfizer or its agent, whenever feasible, to be present during the inspection. The investigator site and investigator will promptly resolve any discrepancies that are identified between the study data and the subject's medical records. The investigator will promptly provide copies of the inspection findings to Pfizer or its agent. Before response submission to the regulatory authorities, the investigator will provide Pfizer or its agents with an opportunity to review and comment on responses to any such findings.

For studies conducted at non-Pfizer investigator sites, it is important that the investigator(s) and their relevant personnel are available during the monitoring visits and possible audits or inspections and that sufficient time is devoted to the process.

10. DATA HANDLING AND RECORD KEEPING

10.1. Case Report Forms/Electronic Data Record

As used in this protocol, the term CRF should be understood to refer to either a paper form or an electronic data record or both, depending on the data collection method used in this study.

A CRF is required and should be completed for each included subject. The completed original CRFs are the sole property of Pfizer and should not be made available in any form to third parties, except for authorized representatives of Pfizer or appropriate regulatory authorities, without written permission from Pfizer. The investigator shall ensure that the CRFs are securely stored at the study site in encrypted electronic and/or paper form and will be password protected or secured in a locked room to prevent access by unauthorized third parties.

The investigator has ultimate responsibility for the collection and reporting of all clinical, safety, and laboratory data entered on the CRFs and any other data collection forms (source documents) and ensuring that they are accurate, authentic/original, attributable, complete, consistent, legible, timely (contemporaneous), enduring, and available when required. The CRFs must be signed by the investigator or by an authorized staff member to attest that the data contained on the CRFs are true. Any corrections to entries made in the CRFs or source documents must be dated, initialed, and explained (if necessary) and should not obscure the original entry.

In most cases the source documents are the hospital or the physician's chart. In these cases, data collected on the CRFs must match those charts.

In some cases, the CRF may also serve as the source document. In these cases, a document should be available at the investigator site and at Pfizer that clearly identifies those data that will be recorded on the CRF, and for which the CRF will stand as the source document.

10.2. Record Retention

To enable evaluations and/or inspections/audits from regulatory authorities or Pfizer, the investigator agrees to keep records, including the identity of all participating subjects (sufficient information to link records, eg, CRFs and hospital records), all original signed informed consent/assent documents, copies of all CRFs, safety reporting forms, source documents, detailed records of treatment disposition, and adequate documentation of relevant correspondence (eg, letters, meeting minutes, and telephone call reports). The records should be retained by the investigator according to the International Conference on Harmonisation (ICH) guidelines, according to local regulations, or as specified in the clinical study agreement (CSA), whichever is longer. The investigator must ensure that the records continue to be stored securely for so long as they are retained.

If the investigator becomes unable for any reason to continue to retain study records for the required period (eg, retirement, relocation), Pfizer should be prospectively notified. The study records must be transferred to a designee acceptable to Pfizer, such as another investigator, another institution, or to an independent third party arranged by Pfizer.

Investigator records must be kept for a minimum of 15 years after completion or discontinuation of the study or for longer if required by applicable local regulations.

The investigator must obtain Pfizer's written permission before disposing of any records, even if retention requirements have been met.

11. ETHICS

11.1. Institutional Review Board/Ethics Committee

It is the responsibility of the investigator to have prospective approval of the study protocol, protocol amendments, informed consent/assent documents, and other relevant documents, eg, recruitment advertisements, if applicable, from the IRB/EC. All correspondence with the IRB/EC should be retained in the investigator file. Copies of IRB/EC approvals should be forwarded to Pfizer.

The only circumstance in which an amendment may be initiated prior to IRB/EC approval is where the change is necessary to eliminate apparent immediate hazards to the subjects. In that event, the investigator must notify the IRB/EC and Pfizer in writing immediately after the implementation.

11.2. Ethical Conduct of the Study

The study will be conducted in accordance with the protocol, legal and regulatory requirements, and the general principles set forth in the International Ethical Guidelines for Biomedical Research Involving Human Subjects (Council for International Organizations of Medical Sciences 2002), ICH Guideline for Good Clinical Practice, and the Declaration of Helsinki.

11.3. Subject Information and Consent

All parties will comply with all applicable laws, including laws regarding the implementation of organizational and technical measures to ensure protection of subject personal data. Such measures will include subject names or other directly identifiable data in any reports, publications, or other disclosures, except where required by applicable laws.

The personal data will be stored at the study site in [encrypted electronic and/or paper] form and will be [password protected or secured in a locked room] to ensure that only authorized study staff have access. The study site will implement appropriate technical and organizational measures to ensure that the personal data can be recovered in the event of disaster. In the event of a potential personal data breach, the study site shall be responsible for determining whether a personal data breach has in fact occurred and, if so, providing breach notifications as required by law.

To protect the rights and freedoms of natural persons with regard to the processing of personal data, when study data are compiled for transfer to Pfizer and other authorized parties, subject names will be removed and will be replaced by a single, specific numerical code, based on a numbering system defined by Pfizer. All other identifiable data transferred to Pfizer or other authorized parties will be identified by this single, subject-specific code. The investigator site will maintain a confidential list of subjects who participated in the study, linking each subject's numerical code to his or her actual identity. In case of data transfer, Pfizer will maintain high standards of confidentiality and protection of subjects' personal data consistent with the Clinical Study Agreement and applicable privacy laws.

The informed consent/assent documents and any subject recruitment materials must be in compliance with ICH GCP, local regulatory requirements, and legal requirements, including applicable privacy laws.

The informed consent/assent documents used during the informed consent process and any subject recruitment materials must be reviewed and approved by Pfizer, approved by the IRB/EC before use, and available for inspection.

The investigator must ensure that each study subject, or parent(s) or legal guardian if a minor, is fully informed about the nature and objectives of the study, the sharing of data relating to the study and possible risks associated with participation, including the risks associated with the processing of the subject's personal data. The investigator further must ensure that each study subject[, or his or her legally acceptable representative, or parent(s) or legal guardian if a minor,] is fully informed about his or her right to access and correct his or her personal data and to withdraw consent for the processing of his or her personal data.

The investigator, or a person designated by the investigator, will obtain written informed consent/assent from each subject or subject's parent(s) or legal guardian before any study-specific activity is performed. The investigator will retain the original of each subject's parent(s) or legal guardian-signed consent/assent document.

12. PUBLICATIONS BY INVESTIGATORS

Pfizer supports the exercise of academic freedom and has no objection to publication by the principal investigator (PI) of the results of the study based on information collected or generated by the PI, whether or not the results are favorable to the Pfizer product. However, to ensure against inadvertent disclosure of confidential information or unprotected inventions, the investigator will provide Pfizer an opportunity to review any proposed publication or other type of disclosure of the results of the study (collectively, "publication") before it is submitted or otherwise disclosed.

The investigator will provide any publication to Pfizer at least 30 days before it is submitted for publication or otherwise disclosed. If any patent action is required to protect intellectual property rights, the investigator agrees to delay the disclosure for a period not to exceed an additional 60 days.

The investigator will, on request, remove any previously undisclosed confidential information before disclosure, except for any study- or Pfizer product-related information necessary to the appropriate scientific presentation or understanding of the study results.

If the study is part of a multicenter study, the investigator agrees that the first publication is to be a joint publication covering all investigator sites, and that any subsequent publications by the PI will reference that primary publication. However, if a joint manuscript has not been submitted for publication within 12 months of completion or termination of the study at all participating sites, the investigator is free to publish separately, subject to the other requirements of this section.

For all publications relating to the study, the institution will comply with recognized ethical standards concerning publications and authorship, including Section II - "Ethical Considerations in the Conduct and Reporting of Research" of the Uniform Requirements for Manuscripts Submitted to Biomedical Journals, <http://www.icmje.org/index.html#authorship>, established by the International Committee of Medical Journal Editors.

Publication of study results is also provided for in the CSA between Pfizer and the institution. In this section entitled Publications by Investigators, the defined terms shall have the meanings given to them in the CSA.

If there is any conflict between the CSA and any attachments to it, the terms of the CSA control. If there is any conflict between this protocol and the CSA, this protocol will control as to any issue regarding treatment of study subjects, and the CSA will control as to all other issues.

Appendix 1. Abbreviations

This following is a list of abbreviations that may be used in the protocol.	
Abbreviation	Term
7vPnC	7-valent pneumococcal conjugate vaccine
13vPnC	13-valent pneumococcal conjugate vaccine
AE	adverse event
CDE	center for drug evaluation
CI	confidence interval
CoP	correlate of protection
CRF	case report form
CSA	clinical study agreement
CSR	clinical study report
DCT	data collection tool
EC	ethics committee
ELISA	enzyme-linked immunosorbent assay
GCP	Good Clinical Practice
GMC	geometric mean concentration
GMR	Geometric mean ratio
GMT	geometric mean titer
ICH	International Conference on Harmonisation
IgG	immunoglobulin G
IPD	invasive pneumococcal disease
IRB	institutional review board
MOPA	multiplex opsonophagocytic activity
N/A	not applicable
NIFDC	National Institutes for Food and Drug Control
PI	principal investigator
SAP	statistical analysis plan
SCH	Suzhou Children's Hospital
UNICEF	United Nations Children's Fund
VE	vaccine effectiveness
VT	vaccine type
WHO	World health organization

1. VERSION HISTORY

Table 1. Summary of Changes

Version/ Date	Associated Protocol Amendment	Rationale	Specific Changes
1/ 18Jul2019	Original (25Jul2018)	N/A	N/A
1.1/16Mar2020	Original (25Jul2018)		Add wording of subset for MOPA testing from Non- 13vPnC cohort and few editorial changes
1.2/22May2020	Original (25Jul2018)		Add wording of handling missing data and immunogenicity data below limit of quantification and a few editorial changes.

2. INTRODUCTION

This statistical analysis plan (SAP) provides the detailed methodology for summary and statistical analyses of the data collected in Study B1851196. This document may modify the plans outlined in the protocol; however, any major modifications of the primary endpoint definition or its analysis will also be reflected in a protocol amendment.

2.1. Study Objectives, Endpoints, and Estimands

To describe the antibody levels as measured by IgG and MOPA by 13vPnC vaccination status and vaccine-type (VT) carriage status, among children 5 months to \leq 60 months of age with diagnosis of clinical pneumonia per local standard

2.1.1. Primary Estimand

The serotype-specific IgG geometric mean concentration (GMC) and MOPA geometric mean titers (GMT) for each of the pneumococcal serotypes measured at the time of diagnosis of clinical pneumonia

The primary estimand of this study will be the GMC and GMT for each cohort (refer to section 2.2 for each cohort). The estimand is defined according to the primary objective and is in alignment with the primary endpoint. It includes the following 2 attributes:

- Population: Patients who meet all study inclusion/exclusion criteria;
- Variable: IgG /MOPA;

2.2. Study Design

This is a cohort study designed to describe serotype-specific antibody levels by 13vPnC vaccination status (in children who completed at least 2 doses of 13vPnC, versus children that did not receive any 13vPnC) and vaccine type (VT) carriage status, among children 5 months to \leq 60 months of age with clinical pneumonia. Thus, there will be four subgroups in this study: the 13vPnC cohort with VT carrier; the 13vPnC cohort without VT carrier; the unvaccinated cohort with VT carrier; and the unvaccinated cohort without VT carrier.

3. ENDPOINTS AND BASELINE VARIABLES: DEFINITIONS AND CONVENTIONS

3.1. Primary Endpoint(s)

The serotype-specific IgG geometric mean concentration (GMC) and MOPA geometric mean titers (GMT) for each of the pneumococcal serotypes measured at the time of diagnosis of clinical pneumonia.

Serum levels of MOPA for each of the 13 pneumococcal serotypes (1, 3, 4, 5, 6A, 6B, 7F, 9V, 14, 18C, 19A, 19F, and 23F) will be determined in all 13vPnC cohort subjects with adequate blood volume. In the non 13vPnC cohort, a sample of subjects with adequate blood volume will be selected, to be equal to the number of the 13vPnC cohort included for MOPA testing. This sample of subjects from Non-13vPnC cohort will be performed by randomly ordering all subjects with adequate serum volume and selecting the first number of subjects which is equal to the number of the 13vPnC cohort included for MOPA testing.

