Prevenar 13, the 13-valent pneumococcal conjugate vaccine (13vPnC) was approved in China in October 2016 for the prevention of invasive pneumococcal disease in infants 6 weeks to 15 months of age. The approved regimen only allows vaccination with Prevenar 13 at 2, 4, 6 months for the primary series and the toddler or booster dose at 12 to 15 months of age. Local serotype coverage in China of 13vPnC can range from 80.5% to as high as 87.2%. There is also some regional difference where Northern China appears to have serotype coverage of 75% as compared to Southern China that has serotype coverage of 92%.⁹⁻¹³

The introduction initially of 7-valent pneumococcal conjugate vaccine (7vPnC) and then of 13vPnC in the national immunization program of various countries reduced dramatically the incidence of invasive and mucosal pneumococcal infections in children.^{14,15} Quantitative serotype-specific anti-capsular polysaccharide immunoglobulin G (IgG) antibody levels of ≥ 0.35 μ g/ml after the primary series are considered to correlate with protection for invasive pneumococcal disease (IPD) and have been used for licensure of 13vPnC.¹⁶ In addition, the amount of antibodies after vaccination and the quality of these antibodies is also important.

The avidity of antibodies is a quality measurement which defines the affinity of antibodies for a particular antigen. An increased avidity is related to a more effective antibody function. Another functional measurement of pneumococcal specific antibodies is its multiplex opsonophagocytic activity (MOPA titers). The primary mechanism for anti-capsular immunity in the host is phagocytosis, through opsonisation by anticapsular antibodies and activation of complement. Functional antibody levels, measured as opsonophagocytic activity, provide valuable additional information for serotype-specific differences in protection.¹⁷ It is generally accepted that higher antibodies are required for the prevention of colonization and mucosal disease caused by vaccine-type *S. pneumoniae*.

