3. STUDY DESIGN

This is a cohort study designed to describe serotype-specific antibody levels by 13vPnC vaccination status (in children who completed at least 2 doses of 13vPnC, versus children that did not receive any 13vPnC) and vaccine type (VT) carriage status, among children 5 months to \leq 60 months of age with clinical pneumonia. Thus, there will be four subgroups in this study: the 13vPnC cohort with VT carrier; the 13vPnC cohort without VT carrier; the unvaccinated cohort with VT carrier; and the unvaccinated cohort without VT carrier.

Children hospitalized with a diagnosis of clinical pneumonia will be considered for the study. Upon identification of a potential subject, all Inclusion and Exclusion criteria will be reviewed. The vaccination history of 13vPnC will initially be obtained either from the patient's parent/caregiver; confirmation of 13vPnC receipt from vaccine book or image of vaccine book is required. If 13vPnC vaccination is confirmed as received, and all other inclusion/exclusion criteria are met, this child will be enrolled and assigned to the vaccinated group. If 13vPnC vaccination is confirmed as not received, and all other inclusion / exclusion criteria are met, this child may be enrolled and assigned to the unvaccinated group. After the subject is enrolled, the 13vPnC receipt date and history of other vaccination status will be recorded, as well as other medical and demographic information. The blood draw of approximately 5 mL will be performed at this time.

Based on SCH local standard practice, deep upper respiratory aspirates are obtained and cultured for children hospitalized with clinical pneumonia. This may occur before the consent or enrollment. If the aspirate was not obtained as part of standard practice, the aspirate will be collected as a study procedure. Once the subject is enrolled, the sample identification (ID) and culture results for this procedure will be recorded into the case report form (CRF). In SCH all *S. pneumoniae* isolates recovered from hospitalized children regardless of patient age will be serotyped by FuDan University as part of study WI232403. Therefore, any additional ID used to label those *S. pneumoniae* isolates will be entered into the CRF so that the serotype information can be imported into this study database.

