5. STUDY PROCEDURES

The study will be conducted at SCH in Suzhou, Jiangsu province. SCH is located in the central area of Gusu district and is the only tier III children's hospital serving most of the young children in Suzhou.

Children who are residents from Suzhou municipal districts (Gusu, New and high-tech, Wuzhong, Xiangcheng, Industrial Park) admitted to the SCH with diagnosis of clinical pneumonia per SCH local standard will be evaluated by investigator.

Inclusion and exclusion criteria will be evaluated and those that fulfill all inclusion criteria and none of the exclusion criteria will be offered to participate in the study. Once Informed Consent has been obtained from parents or legal guardians of participants (vaccinated patient and control), study procedures may start.

If a patient is eligible for this study, all study-related procedures will be conducted by study personnel within one day. For every study subject enrolled in the 13vPnC cohort, two study subjects that did not receive 13vPnC will be enrolled on the same day (or \pm 7 days) into the unvaccinated cohort. These control subjects will be matched by age (5 to \leq 12 months, $>$ 12 to \leq 24 months, $>$ 24 months to \leq 60 months). In other words, for every subject enrolled in the 13vPnC cohort, two subjects within the same age group who did not receive 13vPnC will be enrolled if the non-13vPnC subjects hospital admission dates are within 7 days (\pm) of the vaccinated subjects.

Treatment and non-study procedures will be provided by the patient's physician as per local standard of care.

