5.2. Visit 1 (Enrollment)

1. Enroll the subject to this study, if eligible, and assign the participant to a study cohort.
2. Obtain and record the subject demography (including date of birth, sex, residence, and number/age of siblings, if any).
3. Obtain and record the subject's significant medical history (see [Section 6.1](#)).
4. For 13vPnC subjects, record date(s) of 13vPnC vaccination based on the patient's vaccine book.
5. Record antibiotic usage for the current pneumonia episode, to include antibiotic name, dosage, and start/stop date.
6. Collect a blood sample (approximately 5 mL) within 24 hours of enrollment. Blood must be drawn from peripheral veins (eg, arm, foot, or scalp veins). Drawing blood from central veins (eg, jugular or femoral veins), which may increase the risk associated with study participation, is not permitted.

7. Enter deep upper respiratory aspirate specimen information if this standard procedure was performed for this episode of pneumonia. The sample can be from before or after the enrollment. If an aspirate was not collected as a standard practice, this should be collected as a study procedure. The aspirate should be collected within 24 hours of enrollment.
8. Adverse events (AEs) that occur within 12 hours after the blood draw or aspirate collection (if collected as a study procedure) should be recorded in the source documents and in the AE section of the CRF.
9. The investigator or an authorized designee completes the CRF.

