5.3.1. Immunogenicity Data

Immunogenicity data collected for this study are the results of immunologic assays performed by the National Institutes for Food and Drug Control (NIFDC) on the blood samples collected.

The Lower Limit of Quantitation (LLOQ) in micrograms per mL ($\mu\text{g/mL}$) for each serotype is shown in Table 2.

Table 2. The LLOQ in Micrograms per mL from NIFDC

Serotype	LLOQ
1	0.02
3	0.03
4	0.02
5	0.03
6A	0.03
6B	0.03
7F	0.04
9V	0.02
14	0.04
18C	0.02
19A	0.02
19F	0.03
23F	0.03

Antibody concentrations above LLOQ are considered accurate and their quantitated values will be reported. The Limit of detection (LOD) was established as 50% of the LLOQ. Values below the LLOQ or denoted Below Limit of Quantification (BLQ) will be set to **0.5 \times LOD** for analysis.

The NIFDC's OPA LLOQ in titers for all serotypes was set as 8. For the results of antibody titers that are below the LLOQ, or denoted as BLQ, $0.5 \times \text{LLOQ}$ will be assigned for analysis.

No other missing assay data will be imputed in the analyses. All immunogenicity analyses will be performed after the imputation of the antibody concentrations or antibody titers that are below the LLOQ.

For each serotype's antibody concentrations or antibody titers, the number of subjects with missing values at each blood sampling point will be provided.

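### MOPA is run on serum from hospitalized children who may already be on antibiotics, and the recorded antibiotic data enter no analysis

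*SAP*

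**What the plan says.** The primary endpoint has two measures, IgG GMC and MOPA GMT, for each of 13 serotypes (Protocol 2; SAP 3.1). For the second, SAP 3.1 has "Serum levels of MOPA for each of the 13 pneumococcal serotypes" measured in every 13vPnC child with enough serum and in an equal number of unvaccinated children taken in random order. Antibiotic exposure plays no part in the selection.

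On the source of the serum, Protocol 3 states "Children hospitalized with a diagnosis of clinical pneumonia will be considered for the study", and Protocol 5 adds "Treatment and non-study procedures will be provided by the patient's physician as per local standard of care". Protocol 5.2 times the draw from enrollment only: "Collect a blood sample (approximately 5 mL) within 24 hours of enrollment". The item just before it reads "Record antibiotic usage for the current pneumonia episode, to include antibiotic name, dosage, and start/stop date".

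On low titers, SAP 5.3.1 states "The NIFDC's OPA LLOQ in titers for all serotypes was set as 8" and assigns half of that, 4, to anything below it.

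The antibiotic data are not mentioned again. They are absent from:
- the exclusion criteria (Protocol 4.2), which do bar recent blood products and immunoglobulins;
- the evaluable population (SAP 4);
- the regression covariates (age, residence and season in Protocol 8; age, sex and season in SAP 5.2.2);
- the rules for immunogenicity data (SAP 5.3.1);
- the sensitivity or supplementary analyses (SAP 6.1.2), of which none is planned;
- the baseline summaries (SAP 6.2.1).

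**The concern.** Protocol 1 presents opsonophagocytic activity as a functional measure: "Functional antibody levels, measured as opsonophagocytic activity, provide valuable additional information for serotype-specific differences in protection". An assay of this kind generally reads how many live pneumococci remain after contact with serum. If so, a drug in the serum that kills pneumococci would be read as opsonic activity. The documents do not describe the readout, so this step is an assumption.

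The design makes exposure plausible. The children are inpatients with pneumonia, and no limit is set on the time from admission or first antibiotic dose to the blood draw.

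At stake is the description of functional antibody at disease onset, which Protocol 1 says the regulator asked for. GMTs could be too high, and the comparison of cohorts on MOPA could be distorted. IgG by ELISA does not depend on bacterial killing, so the two primary measures could disagree for a reason unrelated to immunity. No planned table would show why.

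**Working it through.** **Figures in the plan.** None bears directly on this point: there is no target GMR, SD, exposure rate or power statement. The planning figures matter only for cell sizes. Protocol 3.3 gives 3,800 × 2 years × 5% = 380 eligible vaccinated children. At 30% consent, 380 × 0.30 = 114, which the protocol gives as about 100. MOPA is therefore run on about 100 sera per cohort.

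**Inputs.** From SAP 5.3.1: LLOQ 8, and 4 assigned below it. Assumed, because the documents give neither: the share of sera affected and the false titer produced.

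**1. Effect on the unvaccinated GMT.** Suppose all unvaccinated sera are truly below the LLOQ and a fraction f reads a false titer T. Then GMT = 4 × (T/4)^f, so the inflation is (T/4)^f.

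| f | T = 32: 8^f | T = 128: 32^f |
|---|---|---|
| 0.10 | 1.23 | 1.41 |
| 0.20 | 1.52 | 2.00 |
| 0.40 | 2.30 | 4.00 |

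**2. What this means for the cohort GMR.** If no vaccinated serum moves, the GMR is divided by the factor in the table. If a fraction g of vaccinated sera makes the same move, the divisor is (T/4)^(f−g). With T = 32, f = 0.4 and g = 0.2 it is 8^0.2 = 1.52 rather than 2.30. With f = 0.2 and g = 0.1 it is 8^0.1 = 1.23 rather than 1.52. The table is thus an upper bound for shrinkage.

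**3. Drug acting as a minimum apparent titer.** This was simulated with log-normal titers, assumed underlying GMTs of 200 (vaccinated) and 20 (unvaccinated), assumed SD 1.5 on the natural-log scale, and the SAP rule below the LLOQ. Without antibiotic the GMR is 9.3. With equal exposure in both cohorts:

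| Exposed | Minimum 32 | Minimum 64 | Minimum 128 |
|---|---|---|---|
| 10% | 8.7 | 8.4 | 8.1 |
| 30% | 7.5 | 6.7 | 6.0 |
| 60% | 6.1 | 4.9 | 3.9 |

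Low titers are lifted more than high ones, so the GMR moves toward 1 even with balanced exposure. With 60% of vaccinated and 10% of unvaccinated children exposed, and a minimum of 128, it rises slightly instead, from 9.3 to 9.9.

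**4. Drug acting as a constant fold rise k.** The GMR is multiplied by k^(p_vacc − p_unvacc).
- Equal exposure: k^0 = 1, so the GMR is unchanged, although both GMTs are still inflated.
- k = 4, 60% of vaccinated and 30% of unvaccinated exposed: 4^0.3 = 1.52.
- k = 4, exposure the other way round: 4^(−0.3) = 0.66.

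**5. Would excluding exposed sera help?** In the model of step 3 it restores 9.3, because exposure there is independent of true titer.

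**The case against.** - **The mechanism is not in the documents.** Neither document describes the MOPA readout, any serum pre-treatment or any control for non-specific killing. Protocol 6.2 leaves sample-processing detail to a laboratory manual that is not available here. This stands. What is shown is that the protocol and SAP are silent, not that the assay is uncontrolled.
- **The direction is not fixed.** A reader might infer that the MOPA cohort GMR must be pulled toward 1, by nearly the factor by which the unvaccinated GMT rises. The documents do not support that. Shrinkage follows if the drug sets a minimum titer, but a constant fold effect with equal exposure leaves the GMR alone, and heavier exposure among the vaccinated can raise it. Nor can vaccinated titers be assumed high: two doses suffice for entry, children up to 60 months are eligible, and Protocol 1 says circulating antibody declines.
- **A regression term looks like the natural remedy but is not enough.** An exposure main effect imposes one common fold shift. If the effect depends on true titer and exposure is balanced, the cohort coefficient stays close to its distorted value.
- **Exposed and unexposed children may differ in other ways.** Antibiotic use may follow severity or time since onset, so a difference between strata need not be artefact. This also stands, and limits how the extra table can be read.
- **The consequences are limited.** The study is descriptive, with no decision rule. By Protocol 1, the correlate-of-protection estimate uses the effectiveness study and the separate infant immunogenicity study, not these titers. IgG is measured in all children with a blood sample. This lowers the urgency. But description is the study's whole output, and the data needed are largely collected already.

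**Conclusion.** The gap is real: antibiotic exposure is recorded and used nowhere, while one of the two primary measures may be sensitive to it. If residual drug kills the assay bacteria, MOPA GMTs can be inflated. On assumed shares of 10% to 40% and false titers of 32 to 128, the unvaccinated GMT rises 1.23 to 4.00-fold, and the cohort GMR shrinks by at most that factor, less if vaccinated sera also move. The GMR may also be unchanged or raised.

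Three assumptions carry this: that the assay reads bacterial killing, that it has no control for antibiotic, and the assumed shares and false titers. A reader might conclude that the MOPA results are invalid. The documents do not support that, since they show neither the rate of exposure nor the laboratory's procedure. What they support is a cheap check that the SAP omits.

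**What to change.** 1. In SAP 6.2.1, tabulate antibiotic exposure before the blood draw by cohort.
2. In SAP 6.1.2, in place of the current entry, add a supplementary MOPA analysis giving GMTs and cohort GMRs that exclude, or are stratified by, sera drawn on or after the antibiotic start date. Count same-day starts as exposed.
3. At analysis, list sera with MOPA titers at or above the LLOQ across serotypes but IgG below the LLOQ as suspected non-specific killing. The statistician can do this, so exposure data need not go to the laboratory.
4. State that if nearly all sera are exposed, MOPA is reported with this limitation.
5. If the laboratory manual already controls for antibiotic in serum, say so in one SAP sentence. That would settle most of the point.

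The cost is SAP wording, two tables and a listing. Cells will be small: about 200 sera split by cohort and exposure average 50 per cell (200/4), and adding carriage status would bring that to 25 (200/8), with uneven splits. Start and stop are recorded as dates without clock times, so the same-day rule will put some unexposed sera in the exposed group.
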